6.3.1 Study Schedule

6.3.2 Informed Consent

All subjects for this study will be provided a consent form describing this study and providing sufficient information for subjects to make an informed decision about their participation in this study. See Attachment for a copy of the Subject Informed Consent Form.

This consent form will be submitted with the protocol for review and approval to the IRB/EC for the study. The formal consent of a subject, using the IRB/EC-approved consent form, must be obtained before that subject undergoes any study procedure. The consent form must be signed by the subject and the investigator-designated research professional obtaining the consent.

Research coordinator will obtain consent as noted in the standard operating procedure for the consent process. See Attachment

Participants will indicate consent by providing a written or electronic (REDCAP) signature on the Informed Consent Form (ICF) and Health Release Form. REDCAP consent forms are identical to hard copy consents.

Participants will provide a written or electronic signature on the informed consent document prior to any procedures being done specifically for the study. Participants may withdraw consent at any time throughout the course of the trial. A copy of the signed informed consent document will be given to the participants for their records.

A copy of the signed informed consent document will be stored in the subject's research record. The consent process, including the name of the individual obtaining consent, will be thoroughly documented in the subject's research record.

It will not be necessary to use 'Auditor/Witness' and/or translator because persons who consent must be able to read English well enough to understand informed consent and study materials.

6.3.3 Screening

Prescreen

Subjects will be telephone prescreened with an IRB-approved script and prescreen form. The subjects will give verbal consent. The telephone prescreen will take about 10 minutes to conduct and decreases the burden of having subjects come into the clinic to easily screen fail for age, weight or prior medications. The prescreen form of the prescreen failures are destroyed. Those who pass prescreen are given an appointment for the hybrid Screening/Baseline in-remote/clinic visit.

During Screening/Baseline Visit (Week -3-0)

Informed consent will be obtained at the screening visit before any study procedures are conducted. Study staff will review the inclusion and exclusion criteria, collect demographics, medical and psychiatric history via the MINI, prior and concomitant medications, vital signs (pulse and blood pressure) and confirm the ADHD diagnosis via the ACDS v 1.2 and AISRS. Study staff will conduct a physical examination, medical review of systems, and electrocardiogram (ECG). A blood sample will be collected for routine laboratory testing (hematology and blood chemistry) and a urine sample will be collected for urinalysis, urine pregnancy test (for females of child bearing potential), and urine drug screen. Subjects can opt out of these test if they can produce medical records from Primary Care Physician documenting safety tests completed within one year and the Principal Investigator can determine eligibility based on these tests and study screening procedures. Trained Study staff will help with setup and administration of webneuro. Participant will complete self-report forms.

During Baseline:

Principal investigator or co- investigator will review all eligibility criteria, inclusive of inclusion and exclusion criteria. Study staff will review any new concomitant medications or adverse events and a clinician will conduct a C-SSRS. Eligible participant will be given medication information sheet and bottle of blinded placebo.

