	Week -3- 0 Screen	Week -3-0 Screen/BL	Week 1 PbO Lead in	Week 2 PbO Lead in	Week 1	Week 2	Week 3	Week 4	
Consent	x								
Demographics	x								
MINI	x								
ACDS v1.2	x								

AISRS	Х		Х	Х	Х	X	Х	Х	
CGI S	X		X	X	X	Х	X	X	
WEBNEURO; STROOP, GO/NO-GO, CONTINUOUS PERFORMANCE TEST CPT	Х			Х				х	
BRIEF A	Х			X				Х	
EXPANDED ASRS	X		X	X	Х	Х	X	X	
TASS		x	X	X	X	х	X	X	
Medical History		X							
Psychiatric History		x							
Physical Exam		X							

Hematology Chem, UA	X								
Drug Toxicology	Х								
Urine Pregnancy Test	Х								
ECG /EKG Reading	Х								
Review Eligibility		х							
Vital Signs w/ HT/WT	Х		Х	X	X	X	X	X	
C-SSRS		х	X	X	x	x	x	x	
Prior/Con Meds		х	Х	X	X	x	x	x	Х
Adverse Events		х	Х	X	X	X	X	X	х

Dose adjustment	Х	X	X	х	X			
Dispense/High Intensity	х	X	X	х	X	X		
Returns/Drug Account	х	X	X	Х	Х	Х	Х	
Subject reimbursement	х	Х	Х	Х	X	X	Х	

Study Flow Chart

Table of Contents

Synopsis	2
Primary Objective	2
Secondary Objectives	2
Study Duration	2
Study Design	
Study Population	
Number of Participants	
Number of Study Sites	5
Primary Outcome Variables	5
Secondary and Exploratory Outcome Variables	5
Visit Schedule Table	
Study Flow Chart	9
Abbreviations	Error! Bookmark not defined.
Glossary of Terms	Error! Bookmark not defined.
Glossary of Terms 1 - Introduction	Error! Bookmark not defined. 14
Glossary of Terms 1 - Introduction 1.1 Introductory Statement	Error! Bookmark not defined.
Glossary of Terms	Error! Bookmark not defined.
 Glossary of Terms	Error! Bookmark not defined.
 Glossary of Terms	Error! Bookmark not defined. 14
 Glossary of Terms	Error! Bookmark not defined. 14 14 15 15 15 15 15 15
 Glossary of Terms	Error! Bookmark not defined. 14 14 15 15 15 15 15 15 15 15 15 15
 Glossary of Terms	Error! Bookmark not defined. 14 14 15 15 15 15 15 15 15 15 15 15
 Glossary of Terms	Error! Bookmark not defined. 14 14 14 15 15 15 15 17 18 18
 Glossary of Terms	Error! Bookmark not defined. 14 14 14 15 15 15 15 15 15 15 18 18 18 18
 Glossary of Terms	Error! Bookmark not defined. 14 14 15 15 15 15 15 15 18 18 18 18 18 18 19
 Glossary of Terms	Error! Bookmark not defined. 14 14 15 15 15 15 15 15 15 18 18 18 18 18 18 19 20
 Glossary of Terms	Error! Bookmark not defined. 14 14 14 15 15 15 15 15 17 18 18 18 18 18 18 18 18 20 20 20

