6.3 Study Procedures

Study Flow for Hybrid Study Visits.

During Screening/Baseline Visit (Week -3-0)

The screening visit will be conducted and completed in two parts: remote and in-clinic. During the remote portion, informed consent will be obtained at the screening visit before any study procedures are conducted. Study staff will review the inclusion and exclusion criteria, collect demographics, medical and psychiatric history, prior and concomitant medications, and confirm the ADHD diagnosis via the ACDS v 1.2 and AISRS. Subjects will then be placed on a hold in the screening phase, which can last 28 days up to 90 days. Subjects will be re-consented every 30 days and/or at baseline. Subjects will be called every other week during the holding phase to check willingness to continue to participate. During the dual remote/in-clinic portion, study staff will conduct a physical examination, medical review of systems, vital signs (pulse and blood pressure) and electrocardiogram (ECG/EKG). A blood sample will be collected for routine laboratory testing (hematology and blood chemistry) and a urine sample will be collected for urinalysis, urine pregnancy test (for females of child bearing potential), and urine drug screen. All or some of these clinical examinations can be waived from the screening process if subject can provide record from their primary care doctor and the principal investigator approves them. Trained Study staff will conduct the WebNeuro neuropsychological testing. Participant will complete self-report forms.

During Baseline:

Principal investigator or co-investigator will review all eligibility criteria, inclusive of inclusion and exclusion criteria. Study staff will review any new concomitant medications or adverse events and clinician will conduct a C-SSRS. Eligible participant will be given medication information sheet and bottle of blinded placebo.

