1st Dosing information; At the end of Visit -1, eligible participants will begin the singleblind placebo lead-in. Participants will be instructed to take the single-blind placebo the next morning and continue to take IP once daily in the morning and to return all unused capsules at the next study visit. The TASS will be done three times on days of administration. The recommended dosing is at 5 am +/- 1 hour. The first TASS is done at half hour to one-hour post dose (5:30 to 6 am +/- 1 hour), the second TASS is done 4 hours post dose (9am +/- 1 hour) and the third TASS is done 14-15 hours post dose (7pm+/- 1 hour). All TASS administrations will be via telephone.

Placebo Lead-in Phase

Single-Blind Placebo Baseline Lead-in (Week 1, Visit 2)

Eligible participants will return to the study site for the placebo baseline visit within 21-90 days of Visit -1. If unable to come in within the 21 day range, subject will reconsent monthly and have some screening measures redone as per principal investigator discretion. Study staff will review inclusion and exclusion criteria and the results from the ECG, laboratory testing, and urinalysis. The following procedures and assessments will be performed during Visit 1: vital signs, AISRS, Expanded ASRS, CGI-S, and TASS. Concomitant medications and adverse events (AE), if any, will be noted.

At the end of Visit 1, eligible participants will begin the single-blind placebo lead-in. Subjects will be instructed to take the single-blind placebo the next morning, to continue to take IP once daily in the morning and to return all unused capsules at the next study visit. The TASS will be done three times on days of administration. The recommended dosing is at 5 am +/- 1 hour. The first TASS will be done at half hour to one-hour post dose (5:30 to 6 am +/- 1 hour), the second TASS will be done 4 hours post dose (9am +/- 1 hour) and the third TASS will be done 14-15 hours post dose (7pm+/- 1 hour). All TASS administrations will be via telephone.

Single-Blind Placebo Baseline Lead-in (Week 2, Visit 3)

Participants will return to the study site for the second week of Placebo baseline visit within 7 days of Visit 1. The following procedures and assessments will be performed at Visit 2: vital signs, AISRS, CGI-S, WebNeuro battery assessments, TASS, Expanded ASRS, C-SSRS and BRIEF-A. Concomitant medications and AEs, if any, will be noted. Drug accountability and compliance will be performed.

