6.3.5 Study Visits

Study Flow for Hybrid; remote and in clinic visits

During Screening/Baseline Visit (Week -3-0): The screening visit takes about four hours

Informed consent will be obtained at the screening visit before any study procedures are conducted. Study staff will review the inclusion and exclusion criteria, collect demographics, medical and psychiatric history, prior and concomitant medications, vital signs (pulse and blood pressure) and confirm the ADHD diagnosis via the ACDS v 1.2 and AISRS. Study staff will conduct a physical examination, medical review of systems, and electrocardiogram (ECG). A blood sample will be collected for routine laboratory testing (hematology and blood chemistry) and a urine sample will be collected for urinalysis, urine pregnancy test (for females of child bearing potential), and urine drug screen. If available, Principal Investigator will review medical records from Primary Care Physician

documenting safety tests completed within one year to determine continued eligibility based on these tests and study screening procedures. Trained study staff will help set up and administer the webneuro. Participant will complete self-report forms.

During Baseline (Week -3-0): Takes about two to four hours

Principal investigator or co-investigator will review all eligibility criteria, inclusive of inclusion and exclusion criteria. Study staff will review any new concomitant medications or adverse events and clinician will conduct a C-SSRS. Eligible participant will be given medication information sheet and bottle of blinded placebo.

1st Dosing information: At the end of Visit1, eligible participants will begin the singleblind placebo lead-in. Participants will be instructed to take the single-blind placebo the next morning and continue to take IP once daily in the morning and to return all unused capsules at the next study visit. The TASS will be done three times on days of administration. The recommended dosing is at 5 am +/- 1 hour. The first TASS is done at half hour to one-hour post dose (5:30 to 6 am +/- 1 hour), the second TASS is done 4 hours post dose (9am +/- 1 hour) and the third TASS is done 14-15 hours post dose (7pm+/- 1 hour).

Single-Blind Placebo Baseline Lead-in (Week 1, Visit 2): takes approximately two hours.

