6.4.3.3 Safety/Pregnancy-related policy

Throughout this study, we will monitor safety and possible pregnancy by conducting safety clinical tests during screening and eligibility period. We will collect blood tests and urine test to ensure safe participation in the study. In addition, we will conduct the Columbia Suicide Severity Rating Scale (C-SSRS) to evaluate continued mental health and suicidality. We will monitor weekly vital signs (temperature, pulse, respiration, and blood pressure). Adverse events and concomitant medications will also be monitored. All

adverse events will be tabulated in manuscripts with significant testing using the appropriate general linear regression model.

We will report to Shire and our IRB within the necessary times. See section on adverse events. In addition, we will provide pregnant women with a pregnant woman contact sheet and pregnant woman ICF requesting permission to follow pregnant women to pregnancy outcome.

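### Outside primary care records can replace the screening urine pregnancy test and drug screen, with no later test scheduled, so exclusions 5 and 6 can rest on an old result

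*Combined protocol and SAP*

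**What the plan says.** The screening procedures are described three times, and each description lists a urine sample for urinalysis, a pregnancy test where relevant and a drug screen.

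- **Section 6.3.3** follows the list with: "Subjects can opt out of these test if they can produce medical records from Primary Care Physician documenting safety tests completed within one year". The condition is that "the Principal Investigator can determine eligibility based on these tests and study screening procedures".
- **Section 6.3** says that all or some of the examinations "can be waived from the screening process if subject can provide record from their primary care doctor and the principal investigator approves them". It gives no age limit. It also places a waiting period inside screening: "Subjects will then be placed on a hold in the screening phase, which can last 28 days up to 90 days".
- **Section 6.3.5** states no opt-out. It says only: "If available, Principal Investigator will review medical records from Primary Care Physician", again with a one-year window.

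Exclusion 5 in section 5.3.2 bars women who are pregnant, breastfeeding or planning a pregnancy. Exclusion 6 bars anyone with positive urine drug toxicology.

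On later testing, the Visit Schedule Table in the Synopsis marks "Urine Pregnancy Test" once, in the screening block, and does the same for drug toxicology. Section 6.4.3.3 states that "we will monitor safety and possible pregnancy by conducting safety clinical tests during screening and eligibility period". For a subject who cannot return within 21 days, section 6.3 provides for the subject to "have some screening measures redone as per principal investigator discretion".

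**The concern.** The waiver in 6.3 and 6.3.3 directly follows a list that includes both urine tests, and neither test is carved out. An ECG or a routine blood count from some months ago may still be informative. A pregnancy test is different: a negative result from a year ago says nothing about today, because any pregnancy present then would be over. The drug screen raises a similar problem. Exclusion 6 is defined by a urine result, so without a current sample it cannot be applied as written.

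At stake are exposure of an unrecognised pregnancy to an amphetamine and the enforcement of two written exclusions. The drug is a Schedule II product that section 6.1.1 itself describes as open to abuse. Section 7.14 makes pregnancy a reason for discontinuation, but no scheduled test after screening would detect one.

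**Working it through.** **1. Does the waiver reach the two tests?** The three descriptions compare as follows.

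| Section | Urine pregnancy test and drug screen in the list | Outside record may replace the test | Maximum age of record | Investigator's agreement |
|---|---|---|---|---|
| 6.3 | Yes | Yes, all or some | None stated | Must approve |
| 6.3.3 | Yes | Yes | One year | Must be able to determine eligibility |
| 6.3.5 | Yes | Not stated, not ruled out | One year | Reviews records if available |

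Two of the three sections permit the replacement outright, and the three do not agree.

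**2. Does anything later require a test?**

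- Visit Schedule Table: nine columns (two screening/baseline columns, Visits 2 to 7 and the telephone call). Each test is marked in 1 of 9, at screening.
- Visit procedures in 6.3 and 6.3.5: neither test appears at Visits 2 to 7. Visit 2 re-reads the criteria and the existing ECG, laboratory and urinalysis results.
- Baseline eligibility review (6.3, 6.3.3, 6.3.5): no urine test.
- Telephone prescreen (6.3.3), the stage at which 6.1.8 places the drug and alcohol screening: a call of about 10 minutes, so no sample.
- Safety sections 6.2.2 and 6.4.3.3: pregnancy testing is placed in the screening and eligibility period, so these are the tests that can be waived.
- Repeats after a long hold and unscheduled safety laboratory visits (6.3): both depend on the investigator's decision.

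After a waiver, no mandatory test remains.

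**3. How old can the accepted result be?** The plan gives no figure to reproduce, so this is addition from its stated limits. Inputs are a 365-day record limit (6.3.3), a hold of up to 90 days (6.3) and a two-week, 14-day, placebo lead-in (5.1).

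- Age at first placebo = 365 + hold days falling after the point from which the year is counted
- Age at first Mydayis = age at first placebo + 14

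| Year counted from | Hold days added | First placebo | First Mydayis |
|---|---|---|---|
| In-clinic tests, after the hold (the order in 6.3) | 0 | 365 | 365 + 14 = 379 |
| Start of screening, shortest stated hold | 28 | 365 + 28 = 393 | 393 + 14 = 407 |
| Start of screening, longest stated hold | 90 | 365 + 90 = 455 | 455 + 14 = 469 |

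At 30.4 days per month, the range is 12.0 to 15.0 months at first placebo (365/30.4 and 455/30.4) and 12.5 to 15.4 months at first Mydayis (379/30.4 and 469/30.4). Under 6.3 alone there is no upper bound to compute.

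**The case against.** The strongest reply is that this is loose drafting and not a decision to skip testing. Section 6.4.3.3 says blood and urine will be collected, 6.2.2 says pregnancy testing will be done, 6.3.5 lists the sample without an opt-out, and the schedule shows no waiver note. The investigator must also agree, and could properly refuse a year-old pregnancy result as unable to establish eligibility. The criteria are reviewed again at Visit 2, before Mydayis. Breastfeeding and planned pregnancy are established by history, not by a urine test. The consent form, the detailed schedule of events and the medical monitoring plan are listed as appendices but are not available here, and could contain a stricter rule. The longest ages need several conditions to coincide.

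Part of this stands. The case for exclusion 5 is confined to current pregnancy, the upper ages are limits of the text and not expected values, and the conclusion covers only the visible documents.

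The rest does not remove the problem. The sections that state the tests without a waiver show that the text is inconsistent, but they do not cancel the two that grant one. The investigator's discretion is a weak safeguard when 6.3.3 expressly accepts records up to a year old and names no test that must be current. The Visit 2 review adds no new sample.

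**Conclusion.** The concern holds and needs correction. As written, and with the investigator's agreement, the pregnancy part of exclusion 5 and the whole of exclusion 6 can rest on an outside result. Under 6.3.3 that result may be 365 to 455 days old at first placebo and 379 to 469 days old at first Mydayis; under 6.3 it may be of any age. No scheduled test later closes the gap.

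The day counts assume a record at the one-year limit, a two-week lead-in, no discretionary repeat, and a hold that precedes the first placebo, as 6.3 has it. The lead-in text in 6.3 and 6.3.5 measures the interval differently, so the placement of the hold is not fully settled. The start of the one-year window is not stated, which is why a range is given. The number of subjects who would use the waiver is unknown. The weight of the point lies in pregnancy safety and the enforcement of two exclusions; it does not bear on the power calculation or the primary analysis.

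**What to change.** In sections 6.3, 6.3.3 and 6.3.5:

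1. Remove the urine pregnancy test (for women of child-bearing potential) and the urine drug screen from the waiver.
2. Require the study to perform both at screening/baseline, after any hold and before the first placebo bottle is dispensed.
3. Limit the waiver to the other safety tests, such as the ECG and routine blood tests, with the investigator's approval and one maximum record age, set by the investigator and counted from a named visit.
4. Use identical text in all three sections.

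The cost is wording in three places and one urine sample, already in the visit schedule, for each subject who would have used the waiver. Anyone tested before a hold would need a repeat sample. That should be a small number, because 6.3 already places the in-clinic tests after the hold. The convenience of outside records is kept for the remaining tests.

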6.3.4 Recruitment, Enrollment and Retention

This study will accept referrals from other clinicians, provided that the patients have given their clinicians permission to be contacted by the study team or the clinician has provided our contact information to the patient.

We will advertise within and outside New York Langone Medical Center. We use slicer dicer through EPIC to help identify subjects. There are radio and print advertisements created and approved to help with recruitment. We will get subjects that will find us via online search and call the ADHD clinic. We will give them information about the study and then if interested we will conduct the IRB approved prescreen. Trained and qualified research staff will conduct prescreen. Research staff will review prescreen and schedule the potential subject for screening visit.

Subject, if eligible, will be scheduled for a screening visit. If subject request a watermarked copy of the ICF, they can either pick one up or we can email the ICF in a secure e-mail. We will add "safe" in brackets to the subject line. Subject is reminded not to sign that one. The same ICF without the watermark will be provided at the Screening visit for the subject to sign.

Included as appendices or attachment to this protocol are any documents that will be used (letters, telephone scripts, in person introduction scripts, advertisements, emails, letters to the patient's physician or other healthcare provider known to the patient, etc.)

6.3.5 Study Visits

Study Flow for Hybrid; remote and in clinic visits

During Screening/Baseline Visit (Week -3-0): The screening visit takes about four hours

Informed consent will be obtained at the screening visit before any study procedures are conducted. Study staff will review the inclusion and exclusion criteria, collect demographics, medical and psychiatric history, prior and concomitant medications, vital signs (pulse and blood pressure) and confirm the ADHD diagnosis via the ACDS v 1.2 and AISRS. Study staff will conduct a physical examination, medical review of systems, and electrocardiogram (ECG). A blood sample will be collected for routine laboratory testing (hematology and blood chemistry) and a urine sample will be collected for urinalysis, urine pregnancy test (for females of child bearing potential), and urine drug screen. If available, Principal Investigator will review medical records from Primary Care Physician

documenting safety tests completed within one year to determine continued eligibility based on these tests and study screening procedures. Trained study staff will help set up and administer the webneuro. Participant will complete self-report forms.

During Baseline (Week -3-0): Takes about two to four hours

Principal investigator or co-investigator will review all eligibility criteria, inclusive of inclusion and exclusion criteria. Study staff will review any new concomitant medications or adverse events and clinician will conduct a C-SSRS. Eligible participant will be given medication information sheet and bottle of blinded placebo.

1st Dosing information: At the end of Visit1, eligible participants will begin the singleblind placebo lead-in. Participants will be instructed to take the single-blind placebo the next morning and continue to take IP once daily in the morning and to return all unused capsules at the next study visit. The TASS will be done three times on days of administration. The recommended dosing is at 5 am +/- 1 hour. The first TASS is done at half hour to one-hour post dose (5:30 to 6 am +/- 1 hour), the second TASS is done 4 hours post dose (9am +/- 1 hour) and the third TASS is done 14-15 hours post dose (7pm+/- 1 hour).

Single-Blind Placebo Baseline Lead-in (Week 1, Visit 2): takes approximately two hours.

Eligible participants will return to the study site for the placebo-baseline visit within 21 days of Visit1. In some cases subjects can be on hold for 90 days with bimonthly check ins. Study staff will review inclusion and exclusion criteria and the results from the ECG, laboratory testing, and urinalysis. The following procedures and assessments will be performed during Visit 1: vital signs, AISRS, Expanded ASRS, CGI-S, and TASS. Concomitant medications and adverse events (AE), if any, will be noted.

Eligible participants will begin the second week of the single-blind placebo lead-in. Participants will be instructed to take the single-blind placebo the next morning and continue to take IP once daily in the morning and to return all unused caps capsules at the next study visit. The TASS will be done three times on days of administration. The recommended dosing is at 5 am +/- 1 hour. The first TASS is done at half hour to one hour post dose (5:30 to 6 am +/- 1 hour), the second TASS is done 4 hours post dose (9am +/- 1 hour) and the third TASS is done 14-15 hours post dose (7pm+/- 1 hour). All TASS administrations will be via telephone.

Single-Blind Placebo Baseline Lead-in (Week 2, Visit 3): takes approximately two and a half hours.

Participants will return to the study site to finish the second week of placebo lead-in within 7 days of Visit 2. The following procedures and assessments will be performed at

Visit 2: vital signs, AISRS, CGI-S, WebNeuro battery assessments (Verbal Interference/Stroop, Go/No-Go, CPT/TOVA), TASS, Expanded ASRS, C-SSRS and BRIEF-A. Concomitant medications and AEs, if any, will be noted. Drug accountability and compliance will be performed.

Participants with \geq 30% decrease in total AISRS scores during the placebo lead-in will be considered placebo responders and discontinued from the study.

All other participants will be prescribed 12.5mg of Mydayis. They are instructed to take the study medication once daily at 5 am in the morning and to return all unused medication at the next study visit.

The TASS will be done three times on days of administration. The recommended dosing is at 5 am +/- 1 hour. The first TASS is done at half hour to one hour post dose (5:30 to 6 am +/- 1 hour), the second TASS is done 4 hours post dose (9am +/- 1 hour) and the third TASS is done 14-15 hours post dose (7pm+/- 1 hour). All TASS administrations will be via telephone.

Treatment Phase- Hybrid Visits

MYDAYIS Treatment Phase (Weeks 1-4, Visits 4-7): takes approximately two hours.

Participants will return to the study site every 7 days during the MYDAYIS treatment phase. The following procedures and assessments may be performed at Visits 4-7: vital signs, AISRS, CGI-S, WebNeuro battery assessments (Verbal Interference/Stroop, Go/No-Go, CPT/TOVA), TASS, Expanded ASRS, C-SSRS and BRIEF-A. Note; Webneuro and Brief-A only done on visit 7.

Concomitant medications and AEs, if any, will be noted and drug accountability and compliance will be performed. Participants must take 80% of the prescribed doses of study medication in order to be considered compliant.

The TASS will be done three times on days of administration. The recommended dosing is at 5 am +/- 1 hour. The first TASS is done at half hour to one hour post dose (5:30 to 6 am +/- 1 hour), the second TASS is done 4 hours post dose (9am +/- 1 hour) and the third TASS is done 14-15 hours post dose (7pm+/- 1 hour). All TASS administrations will be via telephone.

Participants will receive a re-supply of study medication at the end of every visit during the Mydayis treatment phase. The dose of Mydayis can be clinically adjusted (in the judgment of the investigator) starting at Visit 4 in 12.5 mg/day increments based upon clinical response and side effects, up to a maximal dose of 37.5 mg/day. Participants will be instructed to return all unused medication at each study visit.

Withdrawal/End of Treatment (Visit 7): takes approximately two and a half hours.

Participants will return to the study site for Visit 7 within 7 days of Visit 6. The following procedures and assessments will be performed at Visit 7: vital signs, AISRS, CGI-S,

WebNeuro battery assessments (Verbal Interference/Stroop, Go/No-Go, CPT/TOVA), TASS, Expanded ASRS, C-SSRS and BRIEF-A.

Concomitant medications and AEs, if any, will be noted and drug accountability and compliance will be performed. Participants should report taking at least 80% of the prescribed study medication in order to be considered compliant.

The TASS will be done three times on days of administration. The recommended dosing is at 5am +/- 1 hour. The first TASS is done at half hour to one hour post dose (5:30 to 6 am +/- 1 hour), the second TASS is done 4 hours post dose (9am +/- 1 hour) and the third TASS is done 14-15 hours post dose (7pm+/- 1 hour).

Participants will be given the Adult ADHD Referral list to help with the transitioning into treatment as usual. Those that complete the study, and at the principal investigator's discretion, as a courtesy, can request and receive a letter stating their diagnosis and participation in the study.

GCP FOLLOWUP: Telephone will take about 10-15 minutes

Study staff will make a phone call to the participant within 7 days of Visit 7. Patient will be asked about how they are feeling. Did they transition into treatment as usual? Concomitant medications and AEs, if any, will be noted.

